1.2 STUDY DESIGN

Study BP41316 is a multicenter, randomized, double-blind, parallel-group, 3-arm, placebo-controlled, 12-week treatment Phase II study to investigate the efficacy, safety tolerability, and pharmacokinetics of Alogabat in participants aged 15 to 45 years with a diagnosis of ASD and a Wechsler Abbreviated Scale of Intelligence, Second Edition (WASI-II) score of ≥ 50. Approximately 105 participants with ASD (in order to have at least 84 evaluable participants at study end) aged 15 to 45 years are enrolled into the study. Participants are randomized

in a 1:1:1 ratio (approximately 35 participants randomized to

each treatment arm).

In addition, randomization was staggered with the enrollment of high-functioning adults (defined as WASI-II ≥ 70; [HFA]) first, followed by adolescents and low-functioning adults defined as WASI-II < 70; [LFA]). After approximately 18 high-functioning adults (aged 18 to 45 years) had completed 6 weeks of treatment

together with the SOC conducted a PK, safety, and tolerability review (1st Interim Analysis). Adequate PK, safety, and tolerability in high-functioning adults was established and PK-model predictions from healthy adult volunteers were confirmed to be comparable with the observed PK results in high-functioning adults. Low-functioning adults and adolescents aged 15 to 17 years (both high- and low-functioning) were included in the study. A 2nd Interim Analysis was performed by the IMC + SOC to evaluate PK, safety, and tolerability data from all available participants once 12 adolescents had completed 2 weeks of treatment. Hereby, adequate PK, safety, and tolerability was confirmed in adults and established in adolescents.

Each participant was evaluated using several scales and tests at each visit at the clinic. A total of 9 clinic visits (screening period included) and 1 phone contact, to assess for any clinically significant symptoms and/or new medication, were planned. In addition, digital biomarker data was collected. Each participant needed a reliable caregiver, parent, or support person who oversaw the participant's adherence with protocol-specified procedures and provided feedback on all informant-based assessments throughout the study. The same support person attended all on-site visits. For support persons of high-functioning adult participants, no on-site visits were necessary after the screening visit if the support persons opt to complete all electronic clinical outcome assessments (eCOA), interview, and forms remotely.

The primary analysis will be performed at database lock after Last Participant Last Visit.

1.2.1 Treatment Assignment and Blinding

Randomization took place on Day 1. Randomization to the different treatment arms (placebo, alogabat or alogabat with a ratio of 1:1:1) was stratified by age [adolescents, adults] and IQ [LF, HF], and capping rules were applied as follows:

Table 2 Capping Rules

Clinical Factor	Capping Rule			
IQ (as assessed by WASI-II)	The proportion of low-functioning			
≥ 50 to 69 vs ≥ 70	participants (IQ ≥ 50 to 69) is limited to 25% overall.			
Sex female vs male	The proportion of female participants is limited to a maximum of 25%.			

All participants were centrally assigned to randomized study treatment using an IxRS. Before the study was initiated, the telephone number and call-in directions for the IxRS and/or the login information and directions for the IxRS was provided to each site.

The randomization list was computer generated centrally by a third party and made available only to those individuals responsible for PK sample bioanalysis and to statisticians or programmers at the Sponsor directly involved in the production of outputs to support IMC and SOC meetings. The data was analyzed in a secure area which is not accessible to any blinded personnel.

Blinding

The IxRS was programmed with blind-breaking instructions: The blind may be broken if, in the opinion of the Investigator, it is in the participant's best interest to know the study treatment assignment. The Sponsor must be notified before the blind is broken unless identification of the study treatment is required for a medical emergency in which the knowledge of the specific blinded study treatment will affect the immediate management of the participant's condition (e.g., antidote available). In this case, the Sponsor must be notified within 24 hours after breaking the blind. The date and reason that the blind was broken must be recorded in the source documentation and Clinical Study Report (CSR), as applicable.

Unblinding should not result in the withdrawal of the participants from the study. Every effort should be made to retain unblinded participants. As per Health Authority reporting requirements, the Sponsor will break the treatment code for all unexpected SAEs that are considered by the Investigator to be related to study treatment. Whenever disclosure of the identity of the test medication is necessary, adequate procedures will be in place to ensure integrity of the data.

1.2.2 Independent Review Facility

No Independent Review Facility (IRF) was planned for this study.

1.2.3 Data Monitoring

An IMC consisting of a selected subset of Roche representatives as identified in the "IMC + SOC Agreement" was responsible to perform interim analyses of accumulated safety, tolerability, PK, and efficacy (as required) data. The IMC members, the clinical pharmacologist, and the pharmacometrician were unblinded to individual study treatment allocation.

An SOC consisting of one external expert supported the IMC in making their recommendations. The SOC member was likewise unblinded to individual study treatment allocation. Access to treatment assignment information followed the Sponsor's standard procedures. Based on accumulated study data available at their review, the IMC and SOC could have recommended for example adjustment(s) of the dose levels, dosing regimen, or the timing of dosing. Further details can be found in the "IMC + SOC Agreement".

2. STATISTICAL HYPOTHESES AND SAMPLE SIZE DETERMINATION

2.1 STATISTICAL HYPOTHESES

No formal hypothesis testing will be done. However, to quantify gating criteria it was useful to specify a standardized minimal effect size (MDD) in a way that if the observed drug effect would be above the MDD, a hypothesis test based on p-values of the

ANCOVA models as described in section 3.3 would come out significant, assuming at least 28 subjects are evaluable per arm. Gating criteria will be based on p-values of the ANCOVA models.

2.2 SAMPLE SIZE DETERMINATION

Approximately 105 participants with ASD randomized in a 1:1:1 ratio between two active dosing regimens and placebo need to be recruited in order to obtain evaluable data from approximately 84 participants after 12 weeks of treatment. Evaluable data from 84 ASD participants provides at least 80% power to detect a mean difference between baseline and 12-week follow-up of 4.5 points on a Vineland $^{\text{TM}}$ -3 composite between any active treatment arm and the placebo arm with α = 0.10 error control (1-sided). The minimally detectable difference in this cohort is 2.7 points. It is assumed that the standard deviation of the differences between baseline and 12 weeks follow up is 8.0 points, that 20% of participants will not provide evaluable data, and that the participants recruited will consist of at most 25% low-functioning participants, at most 25% female participants. Because the purpose of this study is exploratory, no adjustment for comparison of multiple active doses to a single placebo arm is performed.

3. ANALYSIS SETS

The analysis data sets for the purposes of analyses are presented in Table 3.

Efficacy analyses based on the Efficacy Analysis Population will be restricted in a way that assessments at week 12 will be excluded from the efficacy analyses if the participant missed more than 7 consecutive study medications immediately preceding the day of the assessment (if performed), or if the overall IMP compliance, i.e. the ratio of administered study medication to planned study medication until the assessment, was < 60%.

Post treatment EEG assessments will be excluded from the PD analysis if the last dose of study medication was taken more than 6 hours before the EEG. Additionally, Week 2 and Week 12 EEG assessments will be excluded from the PD analysis if the study participant missed more than 3 doses in the week preceding the EEG.

Table 3 Analysis Sets

Population	Description
Safety Population	All participants randomized to study treatment and who received at least one dose of the study treatment, whether prematurely withdrawn from the study or not, will be included in the safety analysis.

Pharmacokinetic Population	All participants providing pharmacokinetic data will be included in the PK Population. Participants will be excluded from the PK analysis population if they significantly violate the inclusion or exclusion criteria, deviate significantly from the protocol, or if data are unavailable or incomplete which may influence the PK analysis. Excluded cases will be documented together with the reason for exclusion.
Efficacy Analysis Population	All participants who give informed consent, are randomized, and receive at least one dose of double-blind study medication.

4. STATISTICAL ANALYSES

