9.3 POPULATIONS FOR ANALYSES

For purposes of analysis, the following populations are defined in Table 11.

Table 11 Analysis Populations

Population	Description
Safety	All participants randomized to study treatment and who received at least one dose of the study treatment, whether prematurely withdrawn from the study or not, will be included in the safety analysis.
Pharmacokinetic	All participants providing pharmacokinetic data will be included in the PK Population. Participants will be excluded from the PK analysis population if they significantly violate the inclusion or exclusion criteria, deviate significantly from the protocol, or if data are unavailable or incomplete which may influence the PK analysis. Excluded cases will be documented together with the reason for exclusion. All decisions on exclusions from the analysis will be made prior to database closure.
Efficacy	All participants who give informed consent, are randomized, and receive at least one dose of double-blind study medication. Data will be analyzed as per the actual treatment received.

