1. INTRODUCTION

The objectives of this Phase 2 proof-of-concept study (BP41316) is to investigate the efficacy, safety, and tolerability of Alogabat in adolescents and adults (15 to 45 years of age) with autism spectrum disorder (ASD), with a target on the core symptoms of ASD of social communication deficits, and restricted and repetitive behaviors (RRBs) and interests. In addition, a set of biomarkers linked to the mechanism of action of the study drug or to ASD-related alterations is investigated in a representative patient population to pilot the identification of responder subgroups. To date, very few studies have investigated the effect of pharmacological treatments on the core symptoms of ASD and consequently no pharmacological agents are approved that offer a treatment for the core symptoms in this population of high unmet clinical need.

A key challenge in the development of new therapies to treat the core symptoms in ASD is the change of symptoms across different stages of development in longitudinal studies in both social communication deficits as well as in RRBs (Simonoff et al. 2020; Richler et al. 2010; Pender et al. 2020). The presentation of RRBs is known to be associated with age and the level of intellectual functioning (Lam and Aman 2007, Esbensen et al 2009, Richler et al 2010, Kim and Lord 2010, Uljarevic et al 2022). Thus, interventions may have different effects, depending on age and intelligence quotient (IQ), on individuals with ASD and treatment effects in older adolescents and adults may not be extrapolated to effects in the pediatric population, given the potential difference in manifestations, both quantitatively and qualitatively, of social communication deficits and RRBs with age.

Adolescents and adults aged 15 to 45 years with ASD are enrolled in this study to allow for the generation of data on the safety and tolerability, and the potential efficacy in these age groups.

Analyses of the primary and secondary endpoints as described in the protocol will be performed as planned.

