4.1 GENERAL CONSIDERATIONS

Table 4 Analysis Time Windows

Assessments will be assigned to analysis study days according to visit windows defined below:

Analysis Window Label	Baseline	Day 1	Day 7	Day 14	Day 42	Day 63 (c)	Day 84	
Planned Study Day	1 (a)	1	1	14	42	63	84	
ECGs	ECGs							
Study Day	≤ 1 (a)	1	-	2 to 28	-	-	≥ 71	
Vital Signs,	Vital Signs, KSS							
Study Day	≤ 1 (a)	1	-	2 to 28	29 to 55	-	≥ 71	
Lab (Hematology, Chemistry, Urinalysis)								
Study Day	≤ 1 (a)	-	-	2 to 28 (b)	29 to 55	56 to 70	≥ 71	
ESS								

Study Day	≤ 1	-	-	2 to 28	29 to 70	-	≥ 71			
ESS-CHAD										
Study Day	≤ 1	-	-	2 to 28	29 to 55	56 to 70	≥ 71			
Coagulation	Coagulation									
Study Day	≤ 1 (a)	-	-	-	-	56 to 70	≥ 71			
Vineland-3, RBS-R, CRRI, BAI, PRAS-ASD, SSP, AASP, PedsQL, PROMIS, Anthropometric Measurements										
Study Day	≤ 1 (a)	-	-	-	-	-	≥ 71			
CGI-S, CGI-	l (d)									
Study Day	≤ 1 (a)	-	-	2 to 28 (b)	29 to 70	-	≥ 71			
Neurocogni	itive Battery	/								
Study Day	≤ 1 (a)	1	-	2 to 28 (b)	29 to 70	-	≥ 71			
Sudden Onset of Sleep										
Study Day	≤ 1	-	2 to 10	11 to 28	29 to 55	56 to 70	≥ 71			
(a) Latest assessment prior to intake of first study medication. Use date and time, if available.										

⁽b) May include assessments on day 1 if after the time of first study medication.

If more than one assessment is in the same time window, the assessment that is closest to the planned study day will be selected to enter the summary tables.

Table 5 General Descriptive Statistics

Continuous variables will be summarized with the following descriptive statistics and nomenclature:

n	number of observations or participants
mean	arithmetic mean
SD	standard deviation

⁽c) Planned for adolescent participants only.

⁽d) No baseline for CGI-I.

min	minimum value
q1	first quartile value
median	median value
q 3	third quartile value
max	maximum value

Categorical variables will be summarized and presented with the following nomenclature:

n	frequency
%	percentage

Percentage by category will be based on the number of participants exposed within a category. Categories of NOT REPORTED, MISSING, and/or UNKNOWN will be excluded from summaries if null or n/a.

Besides descriptive summaries, listings, and plots will be provided where deemed necessary. Listings will also include multiple assessments within the same time window.

Table 6 ADaM Datasets

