The analysis datasets will be generated in accordance with Clinical Data Interchange Standard Consortium (CDISC) Analysis Data Model (ADaM) Version 2.1. ADaM compliant datasets will be created by the sponsor.

ADaM Dataset Name	Description	Double Programmed ?
ADSL	Subject Level Analysis Dataset	Yes
ADAE	Adverse Events Analysis Dataset	No
ADCM	Concomitant Medications Analysis Dataset	No
ADMH	Medical History Analysis Dataset	No
ADEX	Exposure Analysis Dataset	No

ADVS	Vital Signs Analysis Dataset	Yes
ADEG	ECG Analysis Dataset	Yes
ADLB	Laboratory Analysis Dataset	No
ADDV	Protocol Deviations Analysis Dataset	No
ADSUB	Subcategory Analysis Dataset	Yes
ADCSSRS	C-SSRS Analysis Dataset	No
ADKSS	KSS Analysis Dataset	No
ADVABS3	VABS-III Questionnaire Analysis Dataset	Yes
ADRBSR	RBS-R Questionnaire Analysis Dataset	Yes
ADESS	ESS Questionnaire Analysis Dataset	No
ADSOSQ	Sudden Onset of Sleep Questionnaire Analysis Dataset	No
ADNEURO	Neurocognitive Battery Analysis Dataset	No
ADCRRI	CRRI Questionnaire Analysis Dataset	Yes
ADCGII	CGI-I Analysis Dataset	Yes
ADCGIS	CGI-S Analysis Dataset	No

ADBAI	BAI Analysis Dataset	Yes
ADPRAS	PRAS-ASD Analysis Dataset	Yes
ADSSP	SSP Analysis Dataset	No
ADAASP	AASP Analysis Dataset	No
ADPROMIS	PROMIS Analysis Dataset	No
ADPEDSQL	PedsQL Analysis Dataset	No

4.1.1 Missing Data

Generally, no data imputations will be made.

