4.2 PRIMARY, SECONDARY AND EXPLORATORY EFFICACY ANALYSIS

The primary efficacy analysis evaluates the mean change from baseline to 12 weeks of treatment as measured by the Vineland-3 ABC three-domain GSV composite. The difference in the mean change from baseline between each of the two active doses and placebo will be extracted as contrasts from the ANCOVA model.

The efficacy analyses of the secondary endpoints and of the CRRI total score evaluate the mean change from baseline to 12 weeks of treatment. The difference in the mean change from baseline of the two active doses and placebo will be extracted as contrasts from the ANCOVA model.

The efficacy analysis of CGI-I evaluates the overall score at 12 weeks of treatment. The difference of the two active doses and placebo will be extracted as contrasts from the ANCOVA model.

4.2.1 Definition of Primary Endpoint

The primary endpoint is Change from baseline to Week 12 in the Adaptive Behavior Composite score of the Vineland[™] Adaptive Behavior Scales, Third Edition (Vineland[™]-3), as defined in Section 1.1 of SAP (see Table 1).

4.2.2 Main Analytical Approach for Primary, Secondary, CRRI and CGI-I Endpoints

The analyses of primary, secondary, CRRI and CGI-I efficacy endpoints will include all participants in the Efficacy Analysis Population.

An analysis of covariance (ANCOVA) model will be used to compare treatment effects for the primary, secondary, CRRI and CGI-I efficacy endpoints across the overall Efficacy Analysis Population of adolescents and adults. The model will include treatment as main effect, individual age at screening, IQ, and baseline score as covariates. Treatment differences will be estimated together with their 80% confidence intervals as derived from the model and their associated p-values.

The ANCOVA model will be applied to change from baseline data y_{ij} of participants i, and treatment $j \in \{\text{placebo (reference)}, \text{low dose}, \text{high dose}\}\)$ as follows:

$$y_{ij}=\mu+t_i+a_i+IQ_i+BL_i+\epsilon_{ij}$$

where μ gives the overall endpoint mean change, followed by the fixed effect t which models the effect of treatment, age a, IQ, the endpoint baseline value BL, and ϵ , which gives the overall error term with $N(0, \sigma_{\epsilon}^2)$.

Table 8 Efficacy Statistical Analysis Methods

Endpoint	Statistical Analysis Methods
Primary	ANCOVA
Secondary	
CRRI, CGI-I	

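### Week-12 efficacy records are dropped on post-randomisation compliance with no unrestricted run planned; separately, the open-ended Day-84 window can label off-drug CGI and safety values as Week 12

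*SAP*

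**What the plan says.** **Compliance rule.** SAP Section 3 carries this restriction: "assessments at week 12 will be excluded from the efficacy analyses if the participant missed more than 7 consecutive study medications immediately preceding" (counted back from the assessment date). A second limb removes the assessment if the ratio of doses taken to doses planned is below 60%. Protocol Table 11 (Section 9.3) defines the efficacy population as "All participants who give informed consent, are randomized, and receive at least one dose of double-blind study medication", with no compliance condition, and SAP Table 3 repeats that definition.

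Elsewhere the SAP says: "Analyses of the primary and secondary endpoints as described in the protocol will be performed as planned" (Section 1); "The analyses of primary, secondary, CRRI and CGI-I efficacy endpoints will include all participants in the Efficacy Analysis Population" (Section 4.2.2); "Generally, no data imputations will be made" (Section 4.1.1); and "Gating criteria will be based on p-values of the ANCOVA models" (Section 2.1). SAP Sections 4.2.2.1 and 4.3 and the Appendix 1 output list plan subgroup estimates, age and IQ interaction models, a CGI-I MMRM and descriptive summaries. None of these lifts the restriction.

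**Day-84 window.** SAP Table 4 assigns every listed assessment from Study Day 71 onward to Day 84. It has no upper limit and no follow-up columns. For the summary tables: "If more than one assessment is in the same time window, the assessment that is closest to the planned study day will be selected". SAP Section 4.2 says: "The efficacy analysis of CGI-I evaluates the overall score at 12 weeks of treatment".

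Protocol Table 1 schedules CGI-S, CGI-I, vital signs and the cognitive battery at both follow-up visits, and ECG and laboratory tests at the 2-week follow-up. Protocol Section 8.11.3 places those visits about 2 and 6 weeks after the last dose.

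**The concern.** **Part 1.** The rule discards outcomes that were collected, using behaviour observed after randomisation. Protocol Section 7.1.1 accepts temporary interruption as a way to manage treatment-related adverse events. A participant who paused for tolerability and still attended Week 12 can therefore be removed, and removals may differ by arm. The comparison is then no longer between the randomised groups even among those assessed.

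Without an unrestricted run or an exclusion table, a reader cannot tell whether a gate was passed or failed because of the rule. The SAP documents and lists exclusions from the PK population but has no equivalent for the primary endpoint.

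The rule's reach is limited. Vineland-3 is not scheduled at early termination, so most early discontinuers have no Week-12 value in any case. The rule acts on those who reached Week 12 after a long gap or with low compliance.

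**Part 2.** A follow-up value taken off drug is not a Week-12 on-treatment value. Under Table 4 as written it takes the Week-12 label if the Week-12 value is missing, and it can displace a valid Week-12 value obtained early in its window. The closest-day rule is stated for summary tables only, so the record that enters the CGI-I ANCOVA is not defined. With no follow-up rows, by-visit summaries of these measures cannot separate on-drug from off-drug values.

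**Working it through.** **Planning figures (SAP Sections 2.1 and 2.2).** Inputs: 84 evaluable, 28 per arm; SD of change 8.0; one-sided alpha 0.10; target difference 4.5; minimally detectable difference (MDD) 2.7; 20% non-evaluable.

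- Standard error = 8 × √(2/28) = 2.138
- MDD = 1.2816 × 2.138 = 2.74 (stated 2.7)
- Power at 4.5 points = Φ(4.5/2.138 − 1.2816) = 79.5% (stated at least 80%)
- 84 / 0.80 = 105 randomised

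The plan's figures reproduce to within rounding.

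**Part 1: shift in an arm mean.** If k of the 28 assessed in an arm are excluded, and their mean change differs by D from those retained, the arm mean moves by k × D / 28 in either direction. The documents give neither k nor D. The values below are assumptions: k from 1 to 4, and D from 4 to 8 points (0.5 to 1 SD).

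| k | D | Shift | Share of 2.7 |
|---|---|---|---|
| 1 | 4 | 0.14 | 5% |
| 1 | 8 | 0.29 | 11% |
| 2 | 8 | 0.57 | 21% |
| 3 | 8 | 0.86 | 32% |
| 4 | 8 | 1.14 | 42% |

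If the 28 are instead the records kept after exclusion, the divisor is 28 + k. The largest shift is then 32/32 = 1.00 point, or 37% of the MDD.

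**Part 1: gate disagreement with no bias.** A simulation used 200,000 trials per cell, three arms of 28, SD 8, a pooled-variance t contrast at one-sided 0.10, and k dropped at random per arm. The restricted and unrestricted gates disagreed this often:

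| True difference | k = 1 | k = 2 | k = 3 |
|---|---|---|---|
| 0 | 2.6% | 3.7% | 4.6% |
| 2.7 | 6.1% | 8.7% | 10.8% |
| 4.5 | 4.5% | 6.6% | 8.5% |

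**Part 2: day pairs.** Protocol Tables 1 and 2 set Week 12 at Day 84 ± 7 (Days 77 to 91) and the 2-week follow-up at the Week 12 visit + 14 ± 7 days. That gives 15 × 15 = 225 permitted pairs. Follow-up falls on Days 84 to 112, always inside the Day-84 window. The 6-week follow-up (Days 112 to 140) is inside it too.

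Follow-up displaces Week 12 when it is closer to Day 84:

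- Week 12 on Day 77, follow-up on Days 84 to 90: 7 pairs
- Week 12 on Day 78, follow-up on Days 85 to 89: 5 pairs
- Week 12 on Day 79, follow-up on Days 86 to 88: 3 pairs
- Week 12 on Day 80, follow-up on Day 87: 1 pair

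The total is 16 pairs. Four more tie: (77, 91), (78, 90), (79, 89) and (80, 88).

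**Does the compliance rule remove such CGI records?** Assume once-daily dosing, a last dose on the Week 12 day, and later days counted as missed. Missed doses before follow-up are then the gap minus 1. Seven of the 16 pairs have a gap of 7 or 8 days, so 6 or 7 missed doses, and are kept. If days after planned dosing do not count as missed, all 16 are kept. The SAP does not say which reading applies, and the rule does not cover safety summaries.

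**Would a simple cap work?** No. All 16 displacing follow-ups fall on Days 84 to 90, so a Day-91 cap removes none of them. It could also cut off a legitimate Week-12 repeat: Protocol Section 8.1.5 allows a repeat within 7 days, so a Day-91 visit can be repeated as late as Day 98.

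**The case against.** On the compliance rule, the case for the plan is that the restriction is prespecified, applies equally to all arms and is lenient. The trial is hypothesis-generating, and an on-treatment question is legitimate in a proof-of-concept study. SAP Section 3 leaves the population definition intact and restricts records within it, so the clash with Section 4.2.2 is softer than a contradiction. The copy of the Appendix 1 output list available for review has gaps. The ANCOVA template does show n by arm, and exposure, disposition and deviation outputs are listed. No gating threshold is stated; one-sided 0.10 is taken from the sample-size section. The values of k and D are assumed, and SD 8.0 and MDD 2.7 are not shown to apply to the growth-scale composite that is analysed. Random deletion shows instability, not bias.

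Much of this limits the size of the point, and the on-treatment run can stay. It does not supply the missing analysis. SAP Sections 4.2 and 4.3 are readable and describe no unrestricted run, and n by arm does not separate dropouts from compliance exclusions.

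On the window, the 16 of 225 are day pairs, not probabilities. Each needs Week 12 at least 4 days early and a follow-up gap of 7 to 13 days; at the planned 14 days, displacement never occurs. A missing Week-12 value is the more realistic route. CGI-I is exploratory in the protocol, and listings keep every record in a window. All of that is right, but the labelling rule as written still puts off-drug values under Week 12.

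**Conclusion.** Both parts hold and should be changed.

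In Part 1, collected Week-12 outcomes are removed on post-randomisation criteria that the protocol does not contain, and no unrestricted comparison or exclusion count is planned. The documents do not determine the size or direction of any bias. Under the stated assumptions an arm mean moves by 0.14 to 1.14 points (5 to 42% of the MDD). Even outcome-neutral exclusions of 1 to 3 per arm change the gate result in about 3 to 11% of trials, depending on the true effect.

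In Part 2, Table 4 is wrong as written for CGI-S, CGI-I, vital signs, the cognitive battery, ECG and laboratory tests. It does not touch Vineland-3, RBS-R or CRRI, which have no scheduled follow-up assessment. How often off-drug values would be used depends on missing and early Week-12 visits, which the documents do not give.

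**What to change.** 1. Run the primary and secondary ANCOVAs on every Week-12 assessment obtained, by randomised arm. Report them beside the compliance-restricted run. Add a table of excluded assessments by arm and reason, and reconcile SAP Sections 1, 3 and 4.2.2 with Protocol Table 11.
2. In SAP Table 4, assign Week-12 and follow-up records by nominal visit and date of last dose, not by study day alone. Keep the protocol's 7-day repeat as part of Week 12, add separate 2-week and 6-week follow-up rows, and state that the same record selection feeds the CGI-I ANCOVA.

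The cost is SAP wording, one more run of existing code and a small table. Including non-adherent participants may slightly dilute the estimated effect, and assignment by nominal visit needs a rule for early-termination visits.
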